1. TITLE

Identifying and examining the effects of source and presentation on responses to electronic cigarette public education messages in young adult vapers and non-vapers – Part 2

2. EXTERNAL IRB REVIEW HISTORY*

NA

3. PRIOR APPROVALS:

The devices are not being tested for safety or effectiveness.

Conflict of Interest (COI):

NA

Clinical Engineering Department:

The sensor devices used in this study have not been evaluated by biomedical engineering.

Biohazardous Agents:

NA

Radiation:

NA

Students as Subjects:

NA

Data Science Core & Recruitment Core:

NA

UMCCTS Protocol Review Committee (PRC)

NA

4. OBJECTIVES*

The goal of the study is to conduct a crowdsourced testing to examine the effects of source and presentation of e-cigarette educational messages among young adults who currently vape and do not vape. The objectives are to examine young adults' self-reported responses toward message source (expert vs. peer), message sidedness (one-sided vs. two-sided), and messages combining both (source x message sidedness) about anti-e-cigarette messages.

Aim 1: To determine the optimal message source and presentation type for young adult vapers and non-vapers to increase acceptance of e-cigarette education messages and e-cigarette harm perceptions.

H1. Vapers will report more optimal psychophysiological responses than peer and two-sided messages.

INVESTIGATOR STUDY PLAN - REQUIRED

H2. Non-vapers will report more optimal psychophysiological responses than expert and one-sided messages.

Please note that all procedures will be done with the appropriate personal protective equipment, which includes a mask and face shield for the researcher. Participants will be required to wear their mask for the entirety of the study.

5. BACKGROUND*

Young adults (18-24-year-olds) in the U.S. have the highest rates of e-cigarette use (vaping),¹ with 16-19% of this population identifying as current users, 44-48% ever users, and 11-16% susceptible never users.² Vaping can lead to nicotine addiction and initiation of cigarette smoking³⁻⁷ and is associated with cognitive and affective disorders among young adults.⁸ The U.S. Food and Drug Administration (FDA) has prioritized educating about the health harm of vaping among young adults. However, young adults may avoid^{9,10} or reject¹¹ the current education messages, especially if they currently vape¹²⁻¹⁴ or perceive the messages as “controlling.”¹⁵ It is urgently needed to increase acceptance of e-cigarette education messages¹⁶ to influence their e-cigarette harm perceptions and vaping behaviors.¹⁷⁻²⁰

Using a trusted source²¹⁻²⁴ and presenting messages appropriately^{25,26} can increase message acceptance. According to persuasion theories, one’s tobacco use status may influence individuals’ response to a source and presentation of messages because vapers and non-vapers differ in their attitudes and personal relevance regarding tobacco use.^{25,27-29} Unfortunately, no research has yet examined the impact of a message source^{22,30} and presentation^{25,31,32} on young adults’ responses to e-cigarette education messages based on their vaping status. Evidence from research with cigarette smokers suggests that vapers will respond defensively to e-cigarette education messages, but non-vapers will not.^{12,33} Vapers may trust a tobacco health information source with similar attributes (e.g., peer young adults)^{29,34} and accept messages with balanced perspectives that both present negative health effects of vaping and acknowledge their potential reasons for vaping (two-sided; e.g., “vaping can be appealing if others are using it, but it can harm your health”).^{25,31,35} On the other hand, non-vapers may trust a source with credentials (e.g., scientists)³⁶⁻³⁸ and accept information-only messages (one-sided; e.g., “vaping can harm your health”).^{13,35} Thus, it is critical to understand and use a trusted source and present messages that are appropriate for vapers and non-vapers to optimize vaping cessation and prevention efforts, making it an important area of study to improve current messaging.

The proposed research is guided by biobehavioral theories of tobacco regulatory science,^{39,40} psychology,^{15,41} and communication.^{42,43} By using previously tested education messages,⁴⁴ we will determine an optimal combination of message source and presentation type to increase message acceptance and e-cigarette harm perceptions. We will compare the effects of two sources (expert and peer) and two message presentation types (one-sided and two-sided) for young adult vapers and non-vapers. We will use in-lab study for objective assessment of psychophysiological measures (heart rate, skin conductance, and eye-tracking) during message exposure (N=112) to determine optimal messaging. The goal of this study is to determine optimal message source and presentation for young adult vapers and non-vapers to increase message acceptance and harm perceptions using psychophysiology.

6. INCLUSION AND EXCLUSION CRITERIA*

INVESTIGATOR STUDY PLAN - REQUIRED

We will recruit young adults (N=112; 18-24 years) from the greater Worcester area, who identify as 1-a) vapers (n=56) or 1-b) susceptible non-vapers (n=56) and fluent in English. All participants will have confirmed 12+ hour abstinence from ingesting tobacco/cannabis prior to beginning the study in the lab

Those who are not fluent in English will not be included in the study. Prisoners will not be included in the study. Pregnant women may be in the study if they choose, but we will not seek pregnant people to be in the study.

7. STUDY-WIDE NUMBER OF SUBJECTS*

NA

8. STUDY-WIDE RECRUITMENT METHODS*

NA

9. STUDY TIMELINES*

An individual's participation in the study will be a 45 minute at a one-time visit. We expect to complete the study within six months of enrolling the first participant.

10. STUDY ENDPOINTS*

The primary outcome measures include psychophysiological responses (cognition, arousal, attention) and self-reported measures of e-cigarette harm message and source perceptions (message acceptance, harm perceptions, reactance, message liking, source trust, attitudes, behavioral intentions).

11. PROCEDURES INVOLVED*

After providing informed consent, participants will be randomized to one of four experimental conditions in a 2 (Source: expert and peer) x 2 (Presentation: one-sided and two-sided) design. Data will be collected through iMotions, a psychophysiological data collection platform. We will track participants' eye movements using an eye-tracking device. We will assess heart rate and skin conductance with a sensor by attaching Velcro-strapped electrodes on the fingers of participant's nondominant hand. When the study begins, participants will complete pretest measures, view messages, during which they will be measured on their psychophysiological responses, and complete posttest measures. Messages (see Appendix-A) will be presented in a random order for at least 10 seconds. Between each message segment, a black screen and "get ready" screen will be presented for 10 seconds to return participants' heartrate and skin conductance levels to baseline. This meets the established amount of time (6 seconds) to collect heart rate and skin conductance.⁴⁵ This procedure will be repeated 18 times for the 18 messages. Finally, participants will complete measures on demographics, attitudes, and behavioral intentions. The entire procedure will take approximately 45 minutes. After completion, participants will be thanked and compensated \$50 for participation. Participants will be extensively debriefed about the hypothetical nature of the message source, the health harms of using any tobacco product, and information about the Massachusetts Tobacco Quitline with contact information. We will provide a consent form and verbally reiterate this information.

In order to minimize subject harm as a result of being shocked by static electricity from the sensors, room temperature will remain above 65 degrees when running participants as the colder,

INVESTIGATOR STUDY PLAN - REQUIRED

drier air is more likely to cause static shock. We will also follow all safety guidelines for the equipment. These include having participants wash their hands thoroughly, then use hand sanitizer, and then use an alcohol towelette to clean the finger the sensor will be placed. In addition, participants will be instructed to try to keep their hand still during the study to ensure the sensor does not move.

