12. DATA AND SPECIMEN BANKING*

NA

13. Data Analysis and Management*

Data will be collected through iMotions, a psychophysiological data collection platform. All data will be saved on a password protected computer on the UMass Chan Medical School server. Upon completion of data collection, all data will be de-identified and stored on the UMass Chan Medical School OneDrive.

Visual inspection of heart rate will be performed prior to statistical analysis to determine if a monophasic pattern resembling a U-shaped pattern is present. Each participant will receive a change in beats per minute (BPM) score based on the second before viewing (baseline) minus each second of the 10-second viewing of the message. Then, the BPM change score will be averaged per theme and compared for the greatest deceleration of heart rate, signifying greater attention to the messages in that theme category. Skin conductance will be analyzed similarly but compared for greatest acceleration, signifying greatest attention. Lastly, dwell time on the message using milliseconds will be calculated for the area of interest within the message. Longest dwell time will signify most visual attention for each message theme category. We will take the mean score for the self-report measures and rank the messages accordingly.

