All study data are collected using the iMotions 6.4 Biometric Research Platform, a secure, computer-based data collection platform. No self-report or psychophysiological data collected are directly linked to participant identifying information: self-report and psychophysiological data collected through iMotions are tracked using a unique, numeric study identifier that does not contain any personally identifying information. A monitor on the computer will track the participant’s eye movements and three sensors on the participant’s fingers will track heart rate and skin conductance. Each message will appear for ten seconds, which falls above the established amount of time needed (6 seconds) to collect heart rate and skin conductance levels for still messages. This will allow us to take into account baseline levels and time for heart rate and skin conductance to react. After each message, participants will answer the same measures included in the participant survey pertaining to responses toward the message and source, and

INVESTIGATOR STUDY PLAN - REQUIRED

perceived message effectiveness. This process will be repeated 18 times for each of the two message sidedness conditions, resulting in a total of 36 different messages seen by participants. Afterwards, participants will be asked to complete additional measures related to actual message effectiveness (e-cigarette attitudes, risk beliefs, intentions to vape).

Between each message sidedness condition, individuals will see a blank black screen for 10 seconds, then a black screen with the words “get ready” for five seconds followed by another black screen for 10 seconds to return heart rate and skin conductance back to baseline. All methods are consistent with accepted standards of psychophysiological measurement for media studies.

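### Scores and ranks ignore presentation position, so any fading of response over the message sequence adds removable noise; the gain from adjusting is small unless the fading is marked

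*Protocol*

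**What the plan says.** Protocol section 11 describes a 2 × 2 randomisation of persons to source and sidedness. Messages "will be presented in a random order", and the section adds: "This procedure will be repeated 18 times for the 18 messages". Between messages, recovery screens "will be presented for 10 seconds to return participants' heartrate and skin conductance levels to baseline".

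Protocol section 13 scores heart rate as a change from the second before each message. "Then, the BPM change score will be averaged per theme and compared for the greatest deceleration of heart rate". Skin conductance is handled in a similar way, dwell time is compared by theme category, and self-report is averaged and used to rank messages. The SAP (Study Design and Power Analysis) assembles responses by message, source and presentation type and ranks them within a multi-attribute decision-making (MADM) framework. Neither document has a term for position, order, fatigue or habituation, and neither says that position is stored.

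Protocol section 26 gives a different sequence: "This process will be repeated 18 times for each of the two message sidedness conditions". By that count each person views 36 messages rather than 18. There the longer pause falls between sidedness conditions: "Between each message sidedness condition, individuals will see a blank black screen for 10 seconds". The order of those two conditions is not stated.

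**The concern.** The main product is a ranking of messages, and the SAP justifies its sample size by the stability of the top 3. Random order prevents systematic favouring of any message, but it does not equalise positions among 7 or 14 viewers. If responses fade as the session goes on, a message that happens to fall early for several viewers gains an advantage unrelated to its content.

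The plan's safeguards deal with something else. The recovery screen and the one-second baseline remove drift in the level of heart rate and skin conductance. They do not correct a response that becomes smaller with repetition, and they do not apply to dwell time or self-report. Because position is randomised, it can be adjusted for safely, and the resulting noise can largely be removed.

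**Working it through.** **Inputs.** From the documents: 18 messages (K = 18), random order, 7 participants per message condition per vaping status, 56 per status, 112 in all. Assumed: each participant gets a fresh random order; the response declines by D residual SDs from first to last message; the true between-message SD is 0.3 residual SD (simulations only). The documents give none of these three.

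**1. The plan's own figure.** 7 × 8 × 2 = 112, taking 8 as the four source directions in Appendix A times two presentation types. With the four conditions named in the text, 7 × 4 × 2 = 56, and 112 then means 14 per condition per status. Both n = 7 and n = 14 are therefore carried forward.

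**2. Chance imbalance in position.** SD of a message's mean position = √((K² − 1)/(12n)).
- n = 7: √(323/84) = 1.96
- n = 14: √(323/168) = 1.39

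By simulation, the earliest-placed and latest-placed of the 18 messages differ on average by 7.3 positions (n = 7) or 5.2 (n = 14).

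**3. Theme averages.** For k messages per theme the variance is divided by k and multiplied by (K − k)/(K − 1). Theme size is not stated. With k = 3 the SD is 1.06 (n = 7) or 0.75 (n = 14); with k = 6 it is 0.67 or 0.48.

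**4. Noise added to message scores.** For a linear decline, the position curve scaled from 1 to 0 has variance (323/12)/17² = 0.0931. Unadjusted error variance is multiplied by 1 + D² × 0.0931 × 18/17.

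**5. Price of adjusting.** Two position terms estimated on (n − 1)(K − 1) degrees of freedom cost about 2/(6 × 17) = 2.0% (n = 7) or 2/(13 × 17) = 0.9% (n = 14).

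| D | Unadjusted variance (no decline = 1) | Divided by adjusted variance (1.020 to 1.009) |
|---|---|---|
| 0 | 1.000 | 0.98 to 0.99 |
| 0.5 | 1.025 | 1.00 to 1.02 |
| 1 | 1.099 | 1.08 to 1.09 |
| 1.64 | 1.265 | 1.24 to 1.25 |

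Simulation agrees: a 1–2% loss at D = 0, about 8% at D = 1 and about 24–26% at D = 1.64. A decline of 1.64 SD means that position explains 20% of within-participant variance: (1.64² × 0.0931)/(1 + 1.64² × 0.0931) = 0.20.

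**6. Effect on the top 3.** Simulated share of the true top 3 recovered, unadjusted then adjusted:
- D = 0: 46.3% and 46.1% (n = 7)
- D = 0.5: 46.2% and 46.0% (n = 7); 54.8% and 55.1% (n = 14)
- D = 1: 44.4% and 45.4% (n = 7); 54.0% and 55.7% (n = 14). These first three lines use linear plus log position. With linear plus a first-message term, D = 1.09 and n = 14 gave 53.9% and 54.5%
- D = 1.64: 43.2% and 46.7% (n = 7); 51.7% and 54.8% or, with the first-message term, 52.4% and 53.9% (n = 14)

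Differences below about 1 point are within simulation noise.

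**7. The 36-message version.** If two blocks of 18 ran in a fixed order, their mean positions would be 9.5 and 27.5. A linear decline of D over 36 messages would shift the one-sided versus two-sided contrast by (27.5 − 9.5)/35 = 0.51 D. That is bias, and more participants would not reduce it.

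**The case against.** The strongest reply is that randomisation already protects the ranking from bias, that the per-message baseline deals with drift, and that no evidence of habituation is offered. Most of this stands. Without a sizeable decline the adjustment gains nothing, and a 1.64 SD fall is a large effect to assume. Averaging by theme also dilutes the noise for heart rate, skin conductance and dwell time, so the message-level figures bear mainly on self-report and on the SAP's merged ranking. What remains is that the baseline does not correct a shrinking response and covers neither dwell time nor self-report.

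A reader might infer three stronger points that the documents do not support:
- That position is already logged. It is plausible for a computer-run platform, but neither document says so.
- That one extra model term would do. Section 13 and the SAP specify averages, ranks and MADM, with no regression model to extend.
- That the source and sidedness comparison is compromised. Under section 11 and the SAP, sidedness varies between persons. If everyone sees all 18 messages, order cancels from each person's overall mean. Position is tied to sidedness only if the section 26 version is the one used and its block order is fixed, and the documents establish neither.

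**Conclusion.** The point holds as an inexpensive, optional gain in precision for message ranks, and a smaller one for theme averages. It is not a flaw in the main between-person contrast. Its size depends on an undocumented decline D: about nil at 0.5 residual SD or less, about 8% in error variance and about 1 point of top-3 recovery at 1 SD, and about 24–26% and 2–3 points at 1.64 SD. If there is no decline, adjusting loses 1–2% of precision. These figures assume a linear decline and independent random orders, and the recovery figures also assume a between-message SD of 0.3. It would be tempting to express the gain as a large saving in participants, but that needs habituation which the documents do not show, and it would overstate the effect on the ranking. The block-order risk is conditional on how the conflict between sections 11 and 26 is resolved.

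**What to change.** 1. State in the protocol that a random order is generated for each participant and that the position of every message is stored.
2. For each message-level outcome (heart rate, skin conductance, dwell time and self-report), prespecify a message-level model with participant, message within condition, and position (linear plus a first-message indicator). A random participant effect keeps differences between conditions in the message means.
3. Use the position-adjusted message means for the theme averages, the ranks and the MADM input.
4. Reconcile section 11 (18 messages, sidedness between persons) with section 26 (36 messages in two sidedness conditions). If two blocks are kept, randomise or counterbalance their order and include it in the model; a position term alone could not cleanly separate a fixed block order from sidedness.

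The cost is a modest amount of extra modelling and the small precision loss above if responses do not fade. No extra participants or visits are needed.

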12. DATA AND SPECIMEN BANKING*

NA

13. Data Analysis and Management*

Data will be collected through iMotions, a psychophysiological data collection platform. All data will be saved on a password protected computer on the UMass Chan Medical School server. Upon completion of data collection, all data will be de-identified and stored on the UMass Chan Medical School OneDrive.

Visual inspection of heart rate will be performed prior to statistical analysis to determine if a monophasic pattern resembling a U-shaped pattern is present. Each participant will receive a change in beats per minute (BPM) score based on the second before viewing (baseline) minus each second of the 10-second viewing of the message. Then, the BPM change score will be averaged per theme and compared for the greatest deceleration of heart rate, signifying greater attention to the messages in that theme category. Skin conductance will be analyzed similarly but compared for greatest acceleration, signifying greatest attention. Lastly, dwell time on the message using milliseconds will be calculated for the area of interest within the message. Longest dwell time will signify most visual attention for each message theme category. We will take the mean score for the self-report measures and rank the messages accordingly.

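### The planned analysis compares message themes and ranks messages, so it cannot test H1 or H2 on source and sidedness in vapers and non-vapers

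*Protocol*

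**What the plan says.** **What is promised.** Protocol section 5 states: "We will compare the effects of two sources (expert and peer) and two message presentation types", for vapers and non-vapers. Aim 1 in section 4 is "To determine the optimal message source and presentation type for young adult vapers and non-vapers". The hypotheses are "H1. Vapers will report more optimal psychophysiological responses than peer and two-sided messages" and "H2. Non-vapers will report more optimal psychophysiological responses than expert and one-sided messages". Section 4 also lists messages combining source and sidedness as an objective, and section 5 seeks the best combination of the two.

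**What is randomised.** Protocol section 11 and the SAP both assign each participant to one of four cells of a source by presentation design. The SAP sets 56 participants per vaping status.

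**What is analysed.** Section 10 gives the outcomes: "The primary outcome measures include psychophysiological responses (cognition, arousal, attention"), plus seven self-report measures. In section 13 the heart-rate step is "Then, the BPM change score will be averaged per theme and compared for the greatest deceleration of heart rate". Skin conductance is treated in a similar way. For eye tracking, "Longest dwell time will signify most visual attention for each message theme category". For self-report, "We will take the mean score for the self-report measures and rank the messages accordingly". The SAP's only analytic method is MADM: responses to each message are stored with source and presentation type, merged with crowdsourced data, and used to rank messages and settle on content.

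**The concern.** The analysis text does not use the factors that the study randomises. Section 13 mentions neither source, sidedness nor vaping status. Its comparison factor is theme, which is not part of the randomised design. In the SAP, vaping status appears only in recruitment and sample size.

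If the plan is followed exactly, the study reports which themes drew the most attention and which messages ranked highest. It does not report how far peer differs from expert, or two-sided from one-sided, among vapers or among non-vapers, nor whether vaping status changes those differences. Any later statement on H1 or H2 would then rest on contrasts chosen after the data were seen, from several outcomes and several possible readings of the hypotheses.

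**Working it through.** **1. Promise against analysis.**

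| Element | Sections 4, 5, 11 and SAP design | Section 13 | SAP method |
|---|---|---|---|
| Source | Randomised, in H1/H2 | Absent | Stored in MADM dataset |
| Sidedness | Randomised, in H1/H2 | Absent | Stored in MADM dataset |
| Vaping status | 56 + 56, in H1/H2 | Absent | Sample size only |
| Theme | Not a design factor | Comparison factor | Absent |
| Output | Comparison of effects | Theme comparison, message ranks | Message ranks |
| Model, contrast, interval or test | – | None | None |

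**2. The plan's own figure.** The SAP bases its size on stable ranks for the top three messages, with 7 participants per message condition per vaping status. The total is reproduced as 7 × 8 × 2 = 112 if a message condition is one of the four source directions in Appendix A crossed with two sidedness levels. That reading is an inference; four conditions would give 7 × 4 × 2 = 56. The rank-stability simulation cannot be repeated because its inputs are not given. On either reading, the criterion concerns message ranks, not the precision of a source or sidedness effect.

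**3. Precision if both factors are between participants** (section 11 and SAP). Assumptions: equal allocation (no ratio is stated), one mean score per participant, and SD taken as the SD of that score.

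- Source or sidedness within one vaping group, 28 vs 28: t(0.975, 54) × √(2/28) = 2.005 × 0.267 = 0.54 SD. A 21 vs 35 split gives 2.005 × √(1/21 + 1/35) = 0.55 SD.
- Interaction of either factor with vaping status, 28 per cell: t(0.975, 108) × √(4/28) = 1.982 × 0.378 = 0.75 SD.
- Source × sidedness interaction within one vaping group, 14 per cell: t(0.975, 52) × √(4/14) = 2.007 × 0.535 = 1.07 SD.
- Noncentral-t power at 28 vs 28 (effect sizes assumed, not from the documents):

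| d | alpha 0.05 | alpha 0.0125 (0.05/4) |
|---|---|---|
| 0.3 | 20% | 8% |
| 0.5 | 45% | 25% |
| 0.8 | 84% | 66% |

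**4. Precision if sidedness is within participants.** Protocol section 26 describes 18 messages in each sidedness condition, 36 in all, whereas section 11 has 18. Source then keeps the 28 vs 28 figures, but sidedness becomes a paired contrast on 56 per group, with half-width t(0.975, 55) × √(2(1 − r)/56):

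- r = 0.3: 2.004 × √(1.4/56) = 0.32 SD; power at d = 0.5 about 87%.
- r = 0.7: 2.004 × √(0.6/56) = 0.21 SD; power at d = 0.5 above 99%.

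The correlations are assumptions. The sidedness interactions also tighten, so 1.07 SD belongs to the between-participant design only. All figures in steps 3 and 4 are participant-level t results, not results for a mixed model.

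**The case against.** The strongest reply is that Aim 1 is a selection aim. The MADM dataset records source and presentation type for every response, and the SAP says that MADM evaluates detail at attribute level as well as in a summary. A ranking keyed in this way can show descriptively which combination comes out on top. That stands, and it rules out a stronger reading that a reader might draw, namely that the plan ignores source and presentation altogether. It does not rescue H1 and H2. The SAP does not say that attributes include source or sidedness, states no split of the ranking by vaping status, and attaches no uncertainty to it. Its opening sentence about assessing which communication principles influence responses is an aim without a method.

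Three further points on that side hold:

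- A reader might count exactly 12 contrasts (2 factors × 2 vaping groups × 3 psychophysiological outcomes). The documents do not fix that number. H1 and H2 have no usable comparator as worded, and they could equally refer to the peer plus two-sided and expert plus one-sided combinations.
- A reader might conclude that every contrast is imprecise. For sidedness this depends on which design is right, as step 4 of the working shows.
- A reader might infer that the theme comparison is an error to be deleted. It can inform the choice of content. The gap is that it stands where the factor comparison should be.

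Finally, the sponsor may prefer not to test hypotheses in a study sized for rank stability. That is legitimate, provided that the hypotheses are reworded to match.

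**Conclusion.** The concern holds in this form: the documents promise source and sidedness comparisons, alone and combined, by vaping status and randomise to those factors, but the stated analyses are a theme comparison and a message ranking. H1 and H2 cannot be tested by following the plan. This is more than missing detail, because section 13 does state an analysis and aims it at a factor that was not randomised. It should be corrected before analysis.

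The conclusion about H1 and H2 rests on the text alone and needs no numerical assumption. The precision figures do depend on assumptions: equal allocation, one score per participant, assumed effect sizes and correlations and, for sidedness, on whether section 11 and the SAP or section 26 describes the real design.

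**What to change.** 1. Reconcile section 11 and the SAP (one of four conditions; 18 messages in section 11) with section 26 (both sidedness conditions, 36 messages). State also whether the source version in Appendix A varies within a participant. These answers determine the random effects.
2. State the comparator in H1 and H2.
3. Add a primary factor-level analysis to section 13 and the SAP. For example: *Outcomes recorded per message will be analysed with a linear mixed model with source, presentation, vaping status and their interactions as fixed effects and random effects for participant and message, matched to the reconciled design. Outcomes measured once will be analysed at participant level. Peer vs expert, two-sided vs one-sided, and the source × sidedness combination will be reported with 95% confidence intervals within vapers and within non-vapers, with the interactions with vaping status.* If section 26 holds, outcomes measured once at the end can be compared by source only.
4. Name one primary psychophysiological outcome and a multiplicity rule for its within-group contrasts; Holm is one option.
5. Keep the theme comparison and the MADM ranking as descriptive outputs.

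If inference is not wanted, restate H1 and H2 as descriptive expectations instead.

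The cost is wording and routine analysis of data already planned, with no new participants or measurements. The downsides are the limited precision shown above, which should be disclosed, and that naming one primary outcome moves the rest of the section 10 list to secondary.
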